## 2.2. Overall Risk/Benefit Assessment

The risk-benefit relationship has been carefully considered in the planning of this trial. Based on preclinical and clinical data available to date, the conduct of the trial is considered safe and reasonable using the dose and schedule of AGEN2034 as specified for Phase 1, Cohort 1 in this clinical trial protocol.

A Safety Monitoring Committee (SMC) in Phase 1 and an Independent Data Monitoring Committee (IDMC) in Phase 2 are planned for ongoing assessment of the risk-benefit ratio. The trial shall be discontinued in the event of any new findings that indicate a relevant deterioration of the risk-benefit relationship and would render continuation of the trial unjustifiable. The risks of exposure to AGEN2034 include:

- Infusion-related reactions.
- Increase in immune-related adverse events (irAEs), which constitute a unique spectrum of AEs that occur via activation of the subject's immune system and that can sometimes lead to serious and even fatal events ([Boutros et al 2016](#); [Kumar et al 2017](#); [Weber et al 2012](#)).

Infusion-related reactions are a risk inherent to administration of any recombinant protein to humans. The incidence of immunogenicity and the character or severity of immunogenicity-induced side effects cannot be predicted by animal models because humanized or fully human proteins usually provoke a much stronger immune-response in rodents or non-human primates

than in humans. However, for AGEN2034, clinical signs of hypersensitivity were not observed in pilot 4-week IV repeat-dose toxicity studies conducted in cynomolgus monkeys (a primate species closer to human). There were also no findings in an in vitro cytokine release assay in human whole blood.

Immune-related AEs are events that are drug-related and can be explained by an immune phenomenon after other etiologies have been ruled out. Relevant clinical safety experience has been generated with several PD-1 pathway-blocking monoclonal antibodies and with the combination with CTLA-4 agents (Ott et al 2017; Boutros et al 2016; Kumar et al 2017).

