- Any Grade 3 drug-related bronchospasm, hypersensitivity reaction, or infusion-related reaction, regardless of duration; with the exception of Grade 3 infusion-related reactions resolving within 6 hours and controlled with medical management;
- Any Grade 3 non-skin, drug-related AE lasting  $>$  7 days, with the following exceptions for uveitis, pneumonitis, bronchospasm, diarrhea, colitis, neurologic toxicity, hypersensitivity reactions, infusion reactions, endocrinopathies, and laboratory abnormalities:
  - Grade 3 drug-related uveitis, pneumonitis, bronchospasm, diarrhea, colitis, neurologic toxicity, hypersensitivity reaction, or infusion reaction of any duration requires discontinuation;
  - Grade 3 drug-related endocrinopathies adequately controlled with only physiologic hormone replacement do not require discontinuation;
  - Grade 3 drug-related laboratory abnormalities do not require treatment discontinuation except:
    - Grade 3 drug-related thrombocytopenia  $>$  7 days or associated with bleeding requires discontinuation;
    - Any drug-related liver function test (LFT) abnormality that meets the following criteria require discontinuation (also see hepatic immune-related AE management algorithm [[Table 7](#)]):

- ▶ AST or ALT  $> 8 \times$  ULN;
- ▶ Total bilirubin  $> 5 \times$  ULN;
- ▶ Concurrent AST or ALT  $> 3 \times$  ULN AND total bilirubin  $> 2 \times$  ULN;
- Any Grade 4 drug-related AE or laboratory abnormality, except for the following events, which do not require discontinuation:
  - Grade 4 neutropenia  $< 7$  days;
  - Grade 4 lymphopenia or leukopenia;
  - Isolated Grade 4 electrolyte imbalances/abnormalities that are not associated with clinical sequelae and are corrected with supplementation/appropriate management within 72 hours after their onset;
- Any AE, laboratory abnormality, or intercurrent illness which, in the judgment of the Investigator, presents a substantial clinical risk to the subject with continued treatment;
- Tumor flare phenomenon, defined as local pain, irritation, or rash localized at sites of known or suspected tumor does not require treatment discontinuation.
- Any requirement for  $\geq 10$  mg per day of prednisone (or equivalent) for  $> 6$  weeks;
- Any recurrence of a Grade 3 or 4 drug-related toxicity;
- Dose delay which results in no AGEN2034 dosing for more than 6 weeks.

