### 5.4.4.2. Treatment Delay

#### 5.4.4.2.1. *Criteria for Treatment Delay*

AGEN2034 administration should be delayed for the following:

- Any Grade  $\geq 2$  non-skin, drug-related AE with the following exceptions:
  - Do not delay treatment for Grade  $\geq 2$  Fatigue and laboratory abnormalities except for:
    - Delay dosing for Grade  $\geq 2$  serum creatinine (more than 1.5x baseline) toxicity
    - If a subject has a baseline AST, ALT, or total bilirubin that is within normal limits, delay dosing for drug-related Grade  $\geq 2$  toxicity;
- Any Grade  $\geq 3$  skin drug-related AE or suspected Stevens-Johnson syndrome (SJS) or toxic epidermal necrolysis (TEN)
- Any Grade  $\geq 3$  drug-related laboratory abnormality with the following exceptions for lymphopenia, AST, ALT, or total bilirubin:
  - Grade 3 lymphopenia does not require a dose delay.
  - If a subject has a baseline AST, ALT, or total bilirubin that is within normal limits, delay dosing for drug-related Grade  $\geq 2$  toxicity.
  - If a subject has baseline AST, ALT, or total bilirubin within the Grade 1 toxicity range, delay dosing for drug-related Grade  $\geq 3$  toxicity.
- Any AE, laboratory abnormality, or inter-current illness which, in the judgment of the investigator, warrants delaying the dose of study drug.

Subjects receiving AGEN2034 who have drug-related toxicities that meet the criteria for dose delay should have treatment delayed until retreatment criteria are met.

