#### 5.4.4.2.2. *Criteria to Resume Treatment*

Subjects may resume treatment with AGEN2034 when drug-related AE(s) resolve(s) to Grade 1 or baseline value, with the following exceptions:

- Subjects may resume treatment in the presence of Grade 2 fatigue.
- Subjects who have not experienced a Grade 3 drug-related skin AE may resume treatment in the presence of Grade 2 skin toxicity.

- Subjects with baseline Grade 1 AST/ALT or total bilirubin who require dose delays for reasons other than a 2-Grade shift in AST/ALT or total bilirubin may resume treatment in the presence of Grade 2 AST/ALT or total bilirubin.
  - Subjects with combined Grade 2 AST/ALT AND total bilirubin values meeting discontinuation parameters ([Section 4.4.1](#)) should have treatment permanently discontinued.
- Drug-related pulmonary toxicity, diarrhea, or colitis must have resolved to baseline before treatment is resumed.
- Drug-related endocrinopathies adequately controlled with only physiologic hormone replacement may resume treatment.
- Subjects who received systemic corticosteroids for management of any drug-related toxicity must be off corticosteroids or have tapered down to an equivalent dose of prednisone  $\leq$  10 mg/day.

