**Table 4: Dermatological Immune-related Adverse Event Management Algorithm**

Dermatological Immune-related Adverse Events		
Grade of Rash (NCI CTCAE v4.03)	Management	Follow-Up
Grade 1–2 Covering ≤30% body surface area.	
 
• Symptomatic therapy (e.g., antihistamines, topical corticosteroids).
 
• Continue AGEN2034 therapy per protocol.
 
	
 
• If persists >1 to 2 weeks or recurs: Consider skin biopsy.
 
• Delay AGEN2034 therapy.
 
• Consider 0.5–1 mg/kg/day methylprednisolone IV or oral equivalent. Once improving, taper corticosteroids over at least 1 month; consider prophylactic antibiotics for opportunistic infections; and resume AGEN2034 therapy per protocol.
 
• If worsens: treat as Grade 3–4.
 

Grade 3–4 Covering >30% body surface area; life-threatening consequences.	
 
• Delay or discontinue AGEN2034 therapy per protocol.
 
• Consider skin biopsy.
 
• Dermatology consult
 
• 1–2 mg/kg/day methylprednisolone IV or oral equivalent.
 
	
 
• If improves to Grade 1: taper corticosteroids over at least 1 month; add prophylactic antibiotics for opportunistic infections.
 
• Resume AGEN2034 therapy per protocol.
 

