**Table 7: Hepatic Immune-related Adverse Event Management Algorithm**

Hepatic Immune-related Adverse Events		
Grade of Liver Test Elevation (NCI CTCAE v4.03)	Management	Follow-Up
Grade 1 AST or ALT >ULN to 3 x ULN and/or total bilirubin >ULN to 1.5 x ULN.	
 
Continue AGEN2034 therapy per protocol.
 
	
 
Continue liver function tests (LFT) monitoring per protocol.
 
If worsens: treat as Grade 2 or Grade 3–4.
 

Grade 2 AST or ALT >3 to ≤5 x ULN and/or total bilirubin >1.5 to ≤3 x ULN.	
 
Delay AGEN2034 therapy per protocol.
 
Increase frequency of monitoring to every 3 days.
 
If subject has concurrent AST or ALT > 3 x ULN AND total bilirubin > 2 x ULN, Discontinue AGEN2034 therapy per protocol.
 
	
 
If returns to baseline: resume routine monitoring; resume AGEN2034 therapy per protocol.
 
If elevations persist >5 to 7 days or worsen: 0.5–1 mg/kg/day methylprednisolone IV or oral equivalent. When LFT returns to Grade 1 or baseline, taper corticosteroids over at least 1 month, consider prophylactic antibiotics for opportunistic infections, and resume AGEN2034 therapy per protocol.
 

Grade 3–4 AST or ALT >5 x ULN and/or total bilirubin >3 x ULN.	
 
Discontinue AGEN2034 therapy per protocol.
 
Increase frequency of monitoring to every 1–2 days.
 
1–2 mg/kg/day methylprednisolone IV or oral equivalent*.
 
Add prophylactic antibiotics for opportunistic infections.
 
Consult gastroenterology.
 
Consider obtaining MRI/CT scan of liver and liver biopsy if clinically warranted.
 
	
 
If returns to Grade 2: taper corticosteroids over at least 1 month.
 
If does not improve in > 3 to 5 days, worsens or rebounds: add mycophenolate mofetil 1 g twice daily. If no response within an additional 3–5 days, consider other immunosuppressants per local guidelines.
 

\*The recommended starting dose for Grade 4 hepatitis is 2 mg/kg/day methylprednisolone IV.

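### For isolated liver-test elevations, Table 7 orders discontinuation where Sections 4.4.1 and 5.4.4.2 allow a hold and rechallenge

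*Protocol*

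**What the plan says.** Three parts of the protocol govern a raised liver test.

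- **Table 7 (Section 5.6.4).** The Grade 3–4 row is defined as "AST or ALT >5 x ULN and/or total bilirubin >3 x ULN". Its action is to discontinue AGEN2034, with the qualifier that this is per protocol. Its follow-up column covers steroid taper and added immunosuppression and says nothing about restarting. The Grade 2 row does say when to restart.
- **Section 4.4.1.** The general rule is that "Grade 3 drug-related laboratory abnormalities do not require treatment discontinuation except" certain cases apply. The liver case reads "Any drug-related liver function test (LFT) abnormality that meets the following criteria require discontinuation", and it lists three criteria: AST or ALT > 8 x ULN; total bilirubin > 5 x ULN; or AST or ALT > 3 x ULN concurrent with total bilirubin > 2 x ULN. The same bullet refers the reader to Table 7.
- **Section 5.4.4.2.** Section 5.4.4.2.1 calls for delay at drug-related Grade ≥ 2 AST, ALT or bilirubin when the baseline value was normal, and at Grade ≥ 3 when it was Grade 1. It adds: "Subjects receiving AGEN2034 who have drug-related toxicities that meet the criteria for dose delay should have treatment delayed until retreatment criteria are met". Section 5.4.4.2.2 then provides: "Subjects may resume treatment with AGEN2034 when drug-related AE(s) resolve(s) to Grade 1 or baseline value". Its only liver-specific bar on restarting concerns "Subjects with combined Grade 2 AST/ALT AND total bilirubin values meeting discontinuation parameters", and it cites Section 4.4.1 for those parameters.

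**The concern.** A subject with an isolated immune-related ALT of 6 x ULN must stop under Table 7. Under Sections 4.4.1 and 5.4.4.2 she is held and may restart on recovery. Both texts apply to her, because Section 2.2 states: "Immune-related AEs are events that are drug-related and can be explained by an immune phenomenon after other etiologies have been ruled out". No rule says which text takes precedence.

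The decision at stake is re-exposure after immune-related liver injury, which is a patient-safety question. Two sites that both follow the protocol can decide it in opposite ways. The choice also determines who appears in the SAP Section 7.6.2 summaries of TEAEs, and of drug-related TEAEs, leading to permanent discontinuation. Those tables will count correctly what happened, but what happened will depend partly on which text a site used.

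**Working it through.** No stated statistical figure depends on this point, so the check is a comparison of rules.

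**1. The rules.** Let A be AST or ALT and B total bilirubin, both in multiples of ULN.

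- Table 7 stops if A > 5, or B > 3, or (A > 3 and B > 2). The last condition stands in its Grade 2 row.
- Section 4.4.1 stops if A > 8, or B > 5, or (A > 3 and B > 2).

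**2. One rule contains the other.** A > 8 implies A > 5, B > 5 implies B > 3, and the concurrent rule is shared. Section 4.4.1 therefore never stops a subject whom Table 7 would not.

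**3. Where they differ.** Section 4.4.1 does not stop when A ≤ 8, B ≤ 5, and either B ≤ 2 or A ≤ 3. Adding the Table 7 stop conditions:

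- if B ≤ 2, Table 7 stops only for A > 5, which gives **zone 1: 5 < A ≤ 8 with B ≤ 2**;
- if A ≤ 3, Table 7 stops only for B > 3, which gives **zone 2: 3 < B ≤ 5 with A ≤ 3**.

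There is no other discordant region.

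| A, B (x ULN) | Table 7 | Section 4.4.1 | Agree? |
|---|---|---|---|
| 6, 1 | stop | not required | no (zone 1) |
| 2, 4 | stop | not required | no (zone 2) |
| 6, 2.5 | stop | stop (concurrent rule) | yes |
| 3.1, 4 | stop | stop (concurrent rule) | yes |
| 8.1, 1 | stop | stop | yes |

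**4. The delay rule covers everyone in the zones.** Inclusion criterion 6b caps entry values at 2.5 x ULN for AST and ALT and 1.5 x ULN for bilirubin. By Table 7's own bands that is at most Grade 1, so one of the two delay rules in Section 5.4.4.2.1 applies to every eligible subject who reaches a zone.

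**5. What discontinue per protocol means elsewhere.** The same wording is used for Grade 3–4 colitis/diarrhea (Table 5), pneumonitis (Table 6) and neurological toxicity (Table 10). For each of these, Section 4.4.1 requires withdrawal at Grade 3 whatever the duration, so the wording means a permanent stop. Where rechallenge is possible the tables show it. Table 4 writes "Delay or discontinue AGEN2034 therapy per protocol" and includes a resume step. Table 9 puts Grade 2–3 creatinine in a delay row with a resume step and keeps discontinuation for Grade 4. Of these rows, only the liver row departs from Section 4.4.1.

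**6. How wide the rechallenge window is.** To restart under Section 5.4.4.2.2, a subject in either zone must return to Grade 1 or baseline and be off steroids or at ≤ 10 mg/day prednisone equivalent. Section 4.4.1 also withdraws anyone whose Grade 2 or 3 toxicity has not resolved within 6 weeks, or who goes more than 6 weeks without a dose. If the no-dosing limit runs from the last dose and the elevation is found at the next 2-weekly visit, about 14 of the 42 days are already used. A full taper of at least 1 month (taken as 30 days) would end no earlier than day 14 + 30 = 44, past the limit. Restarting in time therefore usually depends on reaching ≤ 10 mg/day before the taper is complete. The window is narrow, but it exists.

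**The case against.** The strongest reply is that the texts can be read together. Section 4.4.1 says only that discontinuation is not required, and Section 5.4.4.2.2 says only that subjects may restart, so stopping under Table 7 breaches neither. Table 7 covers the narrower group left after non-inflammatory causes are excluded, where a stricter rule would be coherent, and Section 4.4.1 itself sends the reader there. Alternatively, the per-protocol qualifier and Section 5.6's description of the algorithms as an aid to investigators suggest that Section 4.4.1 governs.

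These two readings point in opposite directions: the first makes Table 7 controlling, the second Section 4.4.1. The cross-reference is circular. Table 7 repeats the concurrent 3 x / 2 x rule but omits the 8 x and 5 x limits, so a site using the table alone cannot know they exist.

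Two points on size do stand. First, Section 4.4.1 withdraws for a Grade 3 non-skin drug-related AE lasting more than 7 days, and its exceptions include laboratory abnormalities but not hepatitis. An event recorded as hepatitis may therefore be stopped under both texts. One recorded as increased ALT, which Section 7.1.2 gives as an example of a reportable AE, may not be. This shrinks the zones without removing them. Second, investigators may already stop for any AE they consider a substantial risk, so some variation between sites is accepted by design.

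**Conclusion.** The inconsistency is real and the protocol should be corrected. It is confined to the two zones in the working. Inside them the outcome differs only for a subject who recovers, meets the steroid condition and meets no other Section 4.4.1 withdrawal criterion. The affected number may be small; the documents give no frequency, so none is estimated. There is no claimed effect on ORR or on the SAP's Hepatitis cluster.

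The conclusion assumes that both zones are Grade 3. The protocol does not print the Grade 3/4 boundary for liver tests, but Section 4.4.1 lists > 8 x and > 5 x ULN as exceptions under its Grade 3 rule, which implies it. In Phase 1 dose escalation the DLT rule could also end treatment for some of these events, so the practical weight lies in Phase 2.

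**What to change.** Rewrite the action in the Table 7 Grade 3–4 row along these lines: delay AGEN2034; discontinue if AST or ALT > 8 x ULN, total bilirubin > 5 x ULN, AST or ALT > 3 x ULN concurrent with total bilirubin > 2 x ULN, or any other Section 4.4.1 withdrawal criterion is met; otherwise resume under Section 5.4.4.2.2.

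If the sponsor wants the stricter > 5 x and > 3 x ULN limits for immune-related liver injury, leave Table 7 as it is and write those limits into Sections 4.4.1 and 5.4.4.2. The choice is clinical, and either version removes the conflict.

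The first version costs one table row in a protocol amendment, with IRB submission across about 60 Phase 2 sites and no new data collection. It openly permits rechallenge after an isolated immune-related elevation, with the Section 4.4.1 rule on recurrent Grade 3 or 4 toxicity as the backstop. SAP Section 4.1 refers to the final stages of enrollment, so the change would mainly protect subjects still on treatment.

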### 5.6.5. Endocrine Immune-related Adverse Events

Rule out non-inflammatory causes, if non-inflammatory cause is identified, treat accordingly and continue therapy per protocol. Consider visual field testing, endocrinology consultation, and imaging.

**Table 8: Endocrine Immune-related Adverse Event Management Algorithm**

Endocrine Immune-related Adverse Events		
Endocrine Disorder	Management	Follow-Up
Asymptomatic thyroid-stimulating hormone (TSH) abnormality	
 
Continue AGEN2034 therapy per protocol.
 
If TSH < 0.5 x lower limit of normal (LLN) or TSH > 2 x ULN, or consistently out of range in 2 subsequent measurements: include free thyroxine (fT4) at subsequent cycles as clinically indicated; consider endocrinology consult.
 
	
Symptomatic endocrinopathy	
 
Evaluate endocrine function.
 
Consider pituitary scan.
 
Symptomatic with abnormal lab/pituitary scan: delay AGEN2034 therapy per protocol; 1-2 mg/kg/day methylprednisolone IV or oral equivalent; initiate appropriate hormone therapy.
 
No abnormal lab/ pituitary MRI scan but symptoms persist: repeat labs in 1-3 wk/MRI in 1 month.
 
	
 
If improves (with or without hormone replacement): taper corticosteroids over at least month and consider prophylactic antibiotics for opportunistic infections.
 
Resume AGEN2034 therapy per protocol.
 
Subjects with adrenal insufficiency may need to continue corticosteroids with mineralocorticoid component.
 

Suspicion of adrenal crisis (e.g., severe dehydration, hypotension, shock out of proportion to current illness)	
 
Delay or discontinue AGEN2034 therapy per protocol.
 
Rule out sepsis.
 
Stress dose of IV corticosteroids with mineralocorticoid activity.
 
IV fluids.
 
Consult endocrinologist.
 
If adrenal crisis ruled out, treat as above for symptomatic endocrinopathy.
 
	

### 5.6.6. Renal Immune-related Adverse Events

Rule out non-inflammatory causes, if non-inflammatory cause is identified, treat accordingly and continue therapy per protocol.

**Table 9: Renal Immune-related Adverse Event Management Algorithm**

Renal Immune-related Adverse Events		
Grade of Creatinine Elevation (NCI CTCAE v4.03)	Management	Follow-Up
Grade 1 Creatinine > upper limit of normal (ULN) and > than baseline but $\leq$ 1.5x baseline.	
 
Continue AGEN2034 therapy per protocol.
 
Monitor creatinine weekly
 
	
 
If returns to baseline: resume routine creatinine monitoring per protocol.
 
If worsens: treat as Grade 2 or Grade 3-4.
 

Grade 2-3 Creatinine > 1.5x baseline to $\leq$ 6x ULN.	
 
Delay AGEN2034 therapy per protocol.
 
Monitor creatinine every 2-3 days
 
0.5 to 1.0 mg/kg/day methylprednisolone IV or oral equivalent.
 
Consider renal biopsy
 
	
 
If returns to Grade 1: taper corticosteroids over at least 1 month, consider prophylactic antibiotics for opportunistic infections, and resume AGEN2034 therapy and routine creatinine monitoring per protocol.
 
If elevations persist <math>></math> 7 days or worsen: treat as Grade 4.
 

Grade 4 Creatinine > 6x ULN.	
 
Discontinue AGEN2034 therapy per protocol.
 
Monitor creatinine daily.
 
1.0 to 2.0 mg/kg/day methylprednisolone IV or IV equivalent.
 
Consult nephrologist.
 
Consider renal biopsy
 
	
 
If returns to Grade 1: taper corticosteroids over at least 1 month and add prophylactic antibiotics for opportunistic infections.
 

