#### **4.4. Criteria for Subject Withdrawal**

##### **4.4.1. Withdrawal from Treatment**

The subject must be withdrawn in the event of any of the following:

- Occurrence of an event that would have been considered an exclusion criterion prior to enrollment, that is clinically relevant and affects the subject's safety, and if discontinuation is considered necessary by the investigator and/or Sponsor.
- Radiological disease progression, defined by RECIST 1.1 as defined in [Section 6.4.4.3](#), unless the subject is considered to derive clinical benefit from the treatment by the investigator, is clinically stable and there is agreement with the Sponsor ([Section 5.4.5](#)).

Clinical stability is defined by:

- Absence of new symptoms and signs indicating clinically significant disease progression
- No decline in ECOG performance status.
- Absence of rapid progression of disease or progressive tumor at critical anatomical sites (e.g., cord compression) requiring urgent alternative medical intervention.

- Note: For Phase 2, tumor assessments should be performed every 6 weeks ( $\pm$  3 days) from first treatment dose until discontinuation of treatment, regardless of reason for discontinuation. This includes patients who are being treated past disease progression. Clinical disease progression, in the absence of radiologic progression on the basis of RECIST 1.1, including 1 or more of the following:
  - signs and/or symptoms of consistent with clinically significant progression of disease, including worsening of laboratory values, appearance of new lesion/worsening of the lesion best seen clinically, etc.
  - decline in ECOG performance status
  - tumor progression at critical anatomical sites that requires urgent medical intervention (e.g., CNS metastasis with potential for cord progression)
  - initiation of chronic opiates, or initiation of chemotherapy or new antineoplastic therapy, palliative radiation therapy, or surgery
- Any Grade 2 drug-related uveitis or eye pain or blurred vision that does not respond to topical therapy and does not improve to Grade 1 severity within 2 weeks OR requires systemic treatment;
- Any Grade  $\geq$  2 drug-related pneumonitis or interstitial lung disease that does not resolve to dose delay and systemic corticosteroids (also see Pulmonary Immune Related Adverse Event Management Algorithm [[Section 5.6.3](#)]);
- Any Grade 2 or 3 drug-related toxicity that does not resolve in  $\leq$  6 weeks;

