**Table 5: Gastrointestinal Immune-related Adverse Event Management Algorithm**

Gastrointestinal Immune-related Adverse Events		
Severity of Diarrhea/Colitis (NCI CTCAE v4.03)	Management	Follow-Up
Grade 1  Diarrhea: <4 stools/day over baseline.  Colitis: asymptomatic.	
 
Continue AGEN2034 therapy per protocol.
 
Symptomatic treatment
 
	
 
Close monitoring for worsening symptoms.
 
Educate subject to report worsening immediately.
 
Consider symptomatic treatment including hydration, electrolyte replacement, dietary changes (e.g. American Dietetic Association colitis diet), and loperamide
 
If worsens: treat as Grade 2 or 3–4.
 

Grade 2  Diarrhea: 4–6 stools per day over baseline; IV fluids indicated <24 h; not interfering with activities of daily living (ADL).  Colitis: abdominal pain; blood in stool	
 
Delay AGEN2034 therapy per protocol.
 
Symptomatic treatment.
 
	
 
If improves to Grade 1: resume AGEN2034 therapy per protocol.
 
If persists >5 to 7 days or recurs: 0.5–1 mg/kg/day methylprednisolone or equivalent.
 
When symptoms improve to Grade 1, taper corticosteroids over at least 1 month; consider prophylactic antibiotics for opportunistic infections; resume AGEN2034 therapy per protocol.
 
If worsens or persists >3 to 5 days with oral corticosteroids: treat as Grade 3–4.
 

Grade 3 to 4  Diarrhea (Grade 3): ≥7 stools per day over baseline; incontinence; IV fluids ≥24 h; interfering with ADL.  Colitis (Grade 3): severe abdominal pain, medical intervention indicated, peritoneal signs.  Grade 4: life-threatening, perforation	
 
Discontinue AGEN2034 therapy per protocol.
 
1–2 mg/kg/day methylprednisolone IV or equivalent.
 
Add prophylactic antibiotics for opportunistic infections.
 
Consider lower endoscopy.
 
	
 
If improves: continue corticosteroids until Grade 1, then taper over at least 1 month.
 
If persists >3 to 5 days, or recurs after improvement: add infliximab 5 mg/kg (if no contraindication). Note: infliximab should not be used in cases of perforation or sepsis.
 

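### For a creatinine rise of Grade 2, or of Grade 3 handled as a laboratory abnormality, Table 9 discontinues study drug after 7 days while Sections 4.4.1 and 5.4.4.2 leave resumption open for up to 6 weeks, and no text says which governs

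*Protocol*

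**What the plan says.** Table 9 of the protocol covers creatinine from more than 1.5 times baseline up to 6 times ULN as one Grade 2-3 row. Its first action is "Delay AGEN2034 therapy per protocol". The follow-up cell allows resumption once creatinine is back to Grade 1, but if the rise persists beyond "7 days or worsen: treat as Grade 4". The Grade 4 row begins "Discontinue AGEN2034 therapy per protocol", and its follow-up cell contains no resumption step.

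Section 4.4.1 is the list of events that compel withdrawal from treatment. It includes "Any Grade 2 or 3 drug-related toxicity that does not resolve in" 6 weeks, and a delay that leaves the subject without dosing for more than 6 weeks. It also has a 7-day rule for Grade 3 non-skin drug-related AEs, from which laboratory abnormalities are carved out: "Grade 3 drug-related laboratory abnormalities do not require treatment discontinuation except" for thrombocytopenia and defined liver-test abnormalities. Creatinine is not among those exceptions.

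Section 5.4.4.2.1 delays dosing for Grade 2 or higher "serum creatinine (more than 1.5x baseline) toxicity". Section 5.4.4.2.2 then says "Subjects may resume treatment with AGEN2034 when drug-related AE(s) resolve(s) to Grade 1 or baseline value". It lists exceptions, but none is renal and none sets a 7-day limit.

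**The concern.** Whether a subject loses study drug permanently can depend on which page the site consults. A creatinine rise that lasts more than a week and then resolves is routed to discontinuation by the organ-specific table, while the general withdrawal and resumption rules leave the subject eligible to restart. Phase 2 plans about 60 centers, so uniform handling cannot be assumed.

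Two planned outputs depend on that handling. SAP Section 7.6.2 tabulates TEAEs, and drug-related TEAEs, leading to permanent treatment discontinuation, and Section 7.6.1 summarizes treatment duration, infusions received and cumulative dose. If sites follow different pages, part of the variation in those tables reflects the wording of the protocol and not the toxicity of the drug.

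**Working it through.** The plan states no figure to reproduce. The check sets the rules side by side and then bounds the period over which they diverge.

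| Drug-related creatinine rise | Table 9 | Sections 4.4.1 and 5.4.4.2 |
|---|---|---|
| Grade 2, up to day 7 | delay | delay |
| Grade 2, day 8 to day 42 | treated as Grade 4: discontinue, no resume step | withdrawal not compelled; may resume at Grade 1 or baseline |
| Grade 3 handled as a laboratory abnormality, day 8 to day 42 | treated as Grade 4: discontinue, no resume step | withdrawal not compelled (laboratory exemption and 6-week limit); may resume at Grade 1 or baseline |
| Grade 3 recorded as a clinical renal AE, beyond day 7 | treated as Grade 4: discontinue | withdrawal compelled by the 7-day rule |
| Grade 2 or 3 unresolved at 6 weeks | already discontinued | withdrawal compelled |

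The conflict is confined to the second and third rows. For Grade 2 it is with the 6-week limit alone, because the laboratory exemption concerns Grade 3. Only persistence is compared here; Table 9 sends a worsening rise to the Grade 4 row as well.

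**Example.** A Grade 2 rise returns to Grade 1 on day 20. Table 9 had sent the subject to discontinuation from day 8. Under Section 5.4.4.2.2 the subject may resume, provided the steroid condition discussed below is met in time.

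**Length of the window.**

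1. Ceiling: 6 weeks = 6 × 7 = 42 days, and 42 − 7 = 35 days (day 8 to day 42).
2. Section 4.4.1 does not say when its 6-week dosing gap starts. Assume it runs from the last dose, and that on the two-weekly Phase 2 schedule the rise begins 0 to 14 days after a dose. Then 42 − 14 = 28 to 42 − 0 = 42 days remain, and the window is 28 − 7 = 21 to 42 − 7 = 35 days.
3. Section 5.4.4.2.2 also requires that a subject given systemic steroids be off them or at 10 mg/day or less of prednisone equivalent. Table 9 gives steroids for Grade 2-3 and tapers them over at least 1 month after return to Grade 1. The documents do not say when in the taper 10 mg/day is reached. As an extreme, assume it takes a full 30 days. With the gap counted from onset, the rise must resolve by day 42 − 30 = 12, which leaves day 8 to day 12, or 5 days. With the gap counted from a dose 14 days before onset, 28 − 30 is negative and the window closes. A faster taper gives values in between.

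**Table 5.** Grade 2 diarrhea or colitis that persists more than 3 to 5 days "with oral corticosteroids: treat as Grade 3–4" reaches a row that also discontinues the drug. The laboratory exemption does not apply there, and Section 4.4.1 already stops Grade 3 diarrhea or colitis at any duration. What remains is a narrower question: Grade 2 events against the 6-week limit.

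**The case against.** The strongest reply is that Section 4.4.1 sets a minimum. Not requiring discontinuation does not forbid it, Section 5.4.4.2.2 is permissive, and Section 4.4.1 has the subject withdrawn for any AE or laboratory abnormality the investigator judges a substantial clinical risk. A site that stops on day 8 breaches none of these. This stands. A reader might infer that the sections give directly opposite orders; they do not. But a site that resumes departs from Table 9 on its face, and the text does not show whether that is a deviation.

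A second reply is that Table 9 defers to Section 4.4.1: its actions are to be taken *per protocol*, and Section 5.6 presents the algorithms as an aid to investigators. Tables 4 and 8 leave delay or discontinuation open in places, which suggests that another section decides. On this reading, treating the rise as Grade 4 changes only monitoring, steroid dose and consultation. The reading is possible but not conclusive. If the rise counts as Grade 4, the Grade 4 laboratory rule in Section 4.4.1 compels discontinuation and has no creatinine exception. If the actual grade counts, the 7-day escalation has no effect on study drug. The protocol does not choose between these, and Section 4.4.1 cross-refers to the pulmonary and hepatic algorithms but not to the renal one.

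A third reply stands for part of the ground. Section 5.6.6 has non-inflammatory causes ruled out, and Section 7.1.2 has a medically important laboratory finding reported as the underlying condition. A Grade 3 event recorded that way falls under the 7-day rule in Section 4.4.1, which agrees with Table 9.

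**Conclusion.** The inconsistency is real and limited to drug-related creatinine rises of Grade 2, and of Grade 3 when handled as a laboratory abnormality. Such a rise that resolves after day 7 and by day 42 at the latest is a discontinuation under Table 9 and may resume under Sections 4.4.1 and 5.4.4.2. The 35 days are an upper bound. The window is 21 to 35 days if the dosing gap runs from the last dose, and shorter again, possibly nil, depending on the steroid taper. No order of precedence is stated.

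Three stronger inferences are not supported.

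- A reader might size the problem from the kidney-injury rate quoted for nivolumab in Section 1.1.3.1. That is serious acute kidney injury in renal cell carcinoma, not a Grade 2-3 creatinine rise lasting over 7 days in cervical cancer. The documents give no frequency for the event in question.
- A reader might expect response follow-up to be lost. Footnote 7 of Table 13 continues scans every 6 weeks after discontinuation for unacceptable toxicity, until centrally established progression.
- A reader might carry the point over to the power of the trial. Nothing here bears on the power figures for ORR.

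What is affected is patient handling, the counts of AEs leading to discontinuation, and exposure.

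**What to change.** Reconcile Section 4.4.1, Section 5.4.4.2, Table 9 and the Grade 2 row of Table 5 in one pass:

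- State whether treating an event as Grade 4 (Table 9) or as Grade 3-4 (Table 5) includes stopping study drug or only the toxicity management in that row.
- For each event, give one time limit after which an unresolved rise or symptom leads to discontinuation.
- Name the section that governs when a management algorithm and Section 4.4.1 differ.

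The clinical team chooses the rule; this review takes no position on which limit is right. The cost is a clarification letter or amendment wording, with no added procedures or data collection.
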